4.4 Safety

All safety summaries will be based on the SS. Any important deviations from the randomised treatment assignment will be listed and considered when interpreting the safety data.

4.4.1.1 Adverse events

All reported AEs will be listed along with the date of onset, date of resolution (if AE is resolved), investigator's assessment of intensity, outcome, action taken with IMP, and possible relationship to study drug.

Any AE occurring before the first dose of IP, or more than 42 days after the last dose of IP, will be considered as non-TEAE, it will be included in the data listings but will not be included in the summary tables of AEs.

Multiple occurrences of a TEAE in the same patient will only be counted once overall considering start date as the first day of first occurrence and stop date the last day of the last occurrence and the TEAE will assigned to the treatment of the first occurrence period study drug. Multiple occurrences of a TEAE in the same patient for the same treatment will only be counted once for that treatment.

The number of patients/event will be tabulated also by preferred term, and treatment.

In the case that, within a treatment period, a patient has more than one episode of the same preferred term with different levels of intensity, action taken, outcome causality or seriousness, then the maximum intensity level, action taken (i.e. withdrawn) and outcome (i.e. fatal), causality level (i.e. related), or seriousness level (i.e. serious), respectively will be used. The following ordering will be used to define maximum intensity level, action taken, outcome causality level, or seriousness level :

- Intensity: Mild < Moderate < Severe
- Causality: No < Yes
- Seriousness: No < Yes

- Action taken: Unknown < Not applicable < Dose not changed < Drug interrupted < Drug withdrawn
- Outcome: Unknown < Recovered/resolved < Recovered/resolved with sequelae < Recovering/resolving < Not recovered/not resolved < Fatal

A general summary of all TEAEs will show the number and percentage of patients with

- Any TEAE
- Any TEAE with outcome = death
- Any TESAE (including events with outcome = death)
- Any TEAE leading to discontinuation of IP
- Any TEAE leading to withdrawal from study

The total number of TEAEs will be presented for the following categories;

- All TEAE
- All TEAE with outcome = death
- All TESAE (including events with outcome = death)
- All TEAE leading to discontinuation of IP
- All TEAE leading to withdrawal from study

The number and percentage of patients who experience one or more TEAEs will be tabulated by treatment and by:

- SOC and PT .
- PT, and maximum reported intensity
- PT, and causality with the IP judged by investigator
- SOC and PT with outcome of death

Additionally, a subset with the number and percentage of patients with any non-serious treatment emergent adverse event (TEAE) by system organ class, and preferred term by treatment with common incidence $\geq 5\%$ will also be produced (ordered by frequency).

Key patient information (age/sex/race) for patients experiencing SAEs and discontinuation of study drug due to AEs will be presented in a listing.

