2. INTRODUCTION

2.1 Study rationale

AZD8871 is a new chemical entity, a muscarinic receptor antagonist and β_2 adrenoceptor agonist (MABA), with the combined properties of a LAMA and a LABA in a single molecule. AZD8871 is being developed as an inhaled long-acting bronchodilator for the maintenance treatment of COPD, formulated as an inhalation powder and delivered by DPI. By combining the activities of a LAMA and a LABA in to a single molecule, AZD8871 aims at providing a novel approach to the treatment of COPD with greater efficacy than single-mechanism bronchodilators, equivalent to LAMA and LABA administered as free- or fixed-dose combination therapies, with an equivalent or superior safety and tolerability profile.

The purpose of this study is to provide efficacy and safety data for AZD8871 in subjects with moderate to severe COPD. This study will determine the 24-hour efficacy (lung function) profile of AZD8871 600 μg relative to placebo DPI based on Trough FEV₁ following repeated dosing (2 weeks). Anoro[®] Ellipta[®] once daily is included as an active control.

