2.1.2 Safety analysis set

The Safety Analysis Set (SS) consists of all randomised patients who receive at least one dose of IP. For summaries based on the SS, patients are included for a treatment only if they received at least one dose of that treatment (e.g. a patient who discontinues prior to taking the study treatment for period 2 will not be included in the safety set for that treatment).

The SS will be used for all summaries of safety data, and patients will be analysed according to the randomised treatment assignment for a given study period. Any important deviations from the randomised treatment assignment and any patients who received IP without being randomised for a given study period will be listed and considered when interpreting the safety data. Relevant safety summaries presented by actual treatment received will be considered if there are a considerable number of patients receiving another treatment than the one they were randomised to.

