3.5 Safety variables

3.5.1 Adverse events

AEs: The number and percentage of patients who experienced 1 or more treatment-emergent adverse event (TEAE), and the number of TEAE occurrences will be tabulated by treatment group. An AE is considered TEAE if the event occurs after first dose of IMP up to 42 days after the administration of the last dose of IMP or was present prior to the date of the first dose of IP, but increased in intensity after IP administration. All events present before first IMP are considered non-TEAEs.

Adverse events occurring before administration of IP (ie, not treatment-emergent) and the number of occurrences will be reported in the same way as TEAEs in a different Table.

A TEAE that occurs during a wash-out period will be associated to the last treatment taken. An AE that occurs more than 42 days after the last IP administration will not be counted as a TEAE.

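### One clause in SAP 4.4.1.1 assigns a recurring TEAE to the treatment of its first occurrence, which contradicts the per-treatment counting required around it

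*SAP*

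**What the plan says.** SAP 4.4.1.1 gives two counting rules in consecutive sentences. The first begins "Multiple occurrences of a TEAE in the same patient will only be counted once overall", takes the start from the first occurrence and the stop from the last, and ends with "the TEAE will assigned to the treatment of the first occurrence period study drug". The second reads "Multiple occurrences of a TEAE in the same patient for the same treatment will only be counted once for that treatment".

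The surrounding text works by treatment or by period:

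- SAP 4.4.1.1 takes the worst intensity, causality, outcome and so on when "within a treatment period, a patient has more than one episode of the same preferred term", and tabulates patients with TEAEs by treatment.
- SAP 2.1.2 builds the safety set treatment by treatment: "patients are included for a treatment only if they received at least one dose of that treatment".
- SAP 3.5.1 requires that "the number of TEAE occurrences will be tabulated by treatment group"; protocol 9.4.2 requires the same.
- SAP 3.5.1 also states: "A TEAE that occurs during a wash-out period will be associated to the last treatment taken".

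On a related point, SAP 3.1.1.2 imputes incomplete AE start dates by comparison with the first dose of IP in the study. None of its rules uses the first dose of the period in which the event occurred.

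**The concern.** In a three-period crossover the same patient can have the same event under two or three treatments, and that recurrence is what the by-treatment AE table has to show. The two sentences disagree in exactly that case. For a headache under both AZD8871 and Anoro, the first rule gives one entry, under whichever came first, and the second gives one entry under each.

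Recurrence across the two actives is plausible. AZD8871 is described as "with the combined properties of a LAMA and a LABA in a single molecule", the comparator is a LAMA/LABA fixed combination, and protocol 2.3 lists known class effects of both mechanisms. AE incidence by treatment is a main safety output, and the SAP leaves the programmer to choose between two rules.

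**Working it through.** **Comparing the rules.** An overall column needs no treatment assignment, so reading the first sentence as covering only that column does not explain why the clause names a treatment. The clause also fits poorly with three other rules: worst levels taken within a period, wash-out events linked to the last treatment taken, and occurrence counts by treatment. SAP section 6, which lists changes from the protocol, does not mention it.

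**Size if the clause were applied.** The plan gives no figure to reproduce and no AE incidences, so the incidences below are assumptions. The design input is six sequences of 12 patients (protocol Table 4), with all periods completed. The recorded incidence of a treatment is the mean over the six sequences of P(event on that treatment and none on an earlier one).

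*Case A, independent events.* With incidence a on the treatment of interest and b, c on the other two, that treatment comes first in two sequences, second in two and third in two:

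recorded = a × [2 + (1−b) + (1−c) + 2(1−b)(1−c)] / 6

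- AZD8871: 0.20 × (2 + 0.85 + 0.90 + 1.53)/6 = 0.1760
- Anoro: 0.15 × (2 + 0.80 + 0.90 + 1.44)/6 = 0.1285
- Placebo: 0.10 × (2 + 0.80 + 0.85 + 1.36)/6 = 0.0835

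*Case B, event fully shared by both actives.* The same 20% of patients have the event on each active; placebo events are independent at 10%. An active records the event only when it precedes the other active (three sequences, one of them with placebo first).

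- Each active: 0.20 × (1 + 1 + 0.9)/6 = 0.0967
- Placebo: 0.10 × (2 + 4 × 0.8)/6 = 0.0867

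*Case C, as B, but placebo events fall in the same susceptible 20%, with probability 0.5.*

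- Each active: 0.20 × (1 + 1 + 0.5)/6 = 0.0833
- Placebo: 0.10 × (2 + 4 × 0)/6 = 0.0333

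| Case | True % (AZD8871/Anoro/placebo) | Recorded % | AZD8871:placebo ratio | Difference, points |
|---|---|---|---|---|
| A | 20/15/10 | 17.6/12.9/8.4 | 2.00 → 2.11 | 10 → 9.3 |
| B | 20/20/10 | 9.7/9.7/8.7 | 2.00 → 1.12 | 10 → 1 |
| C | 20/20/10 | 8.3/8.3/3.3 | 2.00 → 2.50 | 10 → 5 |

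In patients out of 72, a true 14.4 against 7.2 becomes 7.0 against 6.2 in case B and 6.0 against 2.4 in case C. In B and C the two actives stay equal to each other.

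**Incomplete start dates.** This part applies only if imputed dates decide attribution. When only the day is missing and the month is later than that of the study's first dose, the start becomes the 1st of the month. For an on-drug event in Period 2 or 3, that falls before the period's Day 1 unless the event has run into the next month or Day 1 is itself the 1st. With event days uniform over 14 days (mean offset 6.5 days) and the SAP's 30.4-day month:

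1 − 6.5/30.4 − 1/30.4 = 1 − 0.214 − 0.033 = 0.753

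About 75% of such events would therefore be dated into the preceding wash-out and credited to the previous treatment; in Period 1, none. Example: study first dose 22 October 2018, Period 2 Day 1 on 16 December (13 + 42 = 55 days later), event on 21 December with the day missing. It is imputed to 1 December, under the Period 1 treatment.

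**The case against.** The strongest defence is that this is a stray phrase. The next sentence, the within-period rule, the treatment-by-treatment safety set and the occurrence counts all point to per-treatment counting. A careful programmer would follow them and lose nothing. All AEs are listed with onset date, so an error could be found and corrected. That stands, and it keeps the point modest. It does not remove the need to act, because the clause is current text and the overall-column reading does not account for it.

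The magnitude can also be challenged, and here the objection succeeds against stronger readings. From case B a reader might infer that the rule hides a class effect against placebo. That needs every susceptible patient to react to both actives while placebo events are unrelated to susceptibility. No passage supports that combination, and case C moves the ratio the other way. A reader might also infer that by-treatment occurrence counts become impossible. They can still be produced, but would be too low.

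On imputation, a reader might infer that the SAP misattributes three quarters of on-drug events in later periods. The documents do not support this. SAP 3.1.1.2 is framed around treatment-emergent status, for which the study's first dose is the right anchor. No passage says that imputed AE dates decide treatment attribution. The 75% applies only to incomplete dates, and few are expected because start and stop dates and times are collected (protocol 8.3.4) and AEs are reviewed at every visit.

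**Conclusion.** The contradiction in SAP 4.4.1.1 is real and should be removed. If the per-treatment rule governs, as context suggests, the effect is zero. If the clause is applied, by-treatment incidence and occurrence counts are too low wherever events recur across treatments, and in all three cases computed the absolute active-placebo difference shrinks. The ratio has no fixed direction: it depends on how events cluster within patients, and 1.12 and 2.50 are examples under assumed incidences, not bounds. The start-date rule supports only a secondary request for clarification.

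**What to change.** In SAP 4.4.1.1:

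- Delete the assignment to the first-occurrence treatment and the merging from first start to last stop across treatments.
- Attribute each TEAE to the treatment of the period, with its wash-out, in which it starts or worsens.
- Count a patient once per preferred term per treatment, and keep every occurrence in the event counts.
- Restrict counting once overall to any overall column.

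In SAP 3.1.1.2, state whether imputed start dates are used for treatment attribution. If they are, attribute events with incomplete dates from the known date parts and the visit at which they were reported, settled at the blind data review.

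The cost is SAP wording and AE programming, plus a blinded look at the reporting visit for what should be a few events.

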4.4.1.2 Laboratory data

All laboratory data recorded in the eCRF will be listed. Flags will be applied to values falling outside the expanded normal ranges (which will be explicitly noted on these listings where applicable). Individual patient data where ALT and/or AST and total bilirubin are elevated at any time will be listed (ie, ALT and/or AST $\geq 3 \times$ the upper limit of normal [ULN] and total bilirubin $\geq 2 \times$ ULN, at any time) to evaluate potential Hy's Law cases.

Change from baseline to 24h post-dose assessment will be calculated.

For i-STAT glucose and potassium at Day 1 and 14, mean absolute values at baseline, 1, 2, 4, and 24 hours postdose as well as mean changes from baseline at 1, 2, 4, and 24 hours post-dose will be presented by treatment.

Mean absolute values and mean change from baseline for all clinical chemistry and haematology laboratory parameters (in international system of units [SI]) will be presented by treatment and timepoint.

A figure summarizing the mean change from baseline (and SE) in i-STAT glucose and potassium by treatment and timepoint will also be provided.

Shift from baseline tables will be presented by treatment overall and by timepoint, separately for haematology, clinical chemistry and iSTAT measurements, showing the number and percentage of subjects with shifts from baseline for each laboratory variable.

Shift is defined as the change in category based on the expanded normal ranges (low, normal or high as above) at baseline to a post-baseline timepoint. The number and percentage of patients with laboratory test values:

- lower than the lower limit of the expanded normal range (ENR),
- within the ENR limits, and
- larger than the upper limit of the ENR

will be provided for post baseline timepoints, the ENR being calculated by multiplying the LLN and ULN of the laboratory by the factor shown in Table 3.

Moreover, treatment-emergent abnormalities, defined as newly occurring or clinically relevant worsening, as well as notable abnormalities in laboratory parameters will be summarised by means of shift contingency tables comparing the values assessed at post-baseline timepoints to the baseline values; values at baseline are "Low", "Normal", "High" according to Table 3; values post-baseline are "New", "Worsened", "Notable". Newly occurring or clinically relevant worsening laboratory abnormalities in laboratory parameters will be identified using the ENR. A laboratory result lying outside the ENR will be considered abnormal.

A laboratory parameter will be defined as showing a “New” abnormality if the observed lab test value is within the ENR at baseline but not at post-baseline timepoints, or it is outside the ENR at baseline and outside the ENR at endpoint at different extreme limits (from expanded lower limit to expanded upper limit, or vice versa).

A laboratory parameter will be defined as “Worsened” if the baseline lab test value is above the expanded upper limit of the corresponding normal range (xULN) specified in Table 3 and the ratio of endpoint value to baseline value is also greater than the corresponding coefficient (multiplying factor) specified in Table 3, or alternatively if the baseline laboratory test value is below the expanded lower limit of the corresponding normal range (xLLN) specified in the above table and the ratio of endpoint value to baseline value is also lower than the corresponding coefficient specified in Table 3.

The laboratory abnormality will be also classified as a “Notable” abnormality if it satisfies the criteria detailed in Table 3.

A listing of all treatment-emergent AEs recorded for patients with laboratory parameters outside of the ENR limits (at baseline or post-baseline) will also be provided including the assessment of clinical relevance by investigator.

Pregnancy test results will be listed only.

Table 3 Expanded normal ranges and notable abnormalities for laboratory parameters

Laboratory Parameter	Expanded Normal Ranges		Notable Abnormalities	
	Lower Limit	Upper Limit	Lower Limit	Upper Limit
HAEMATOLOGY				
Hemoglobin	0.85 × LLN	1.15 × ULN	< 60 g/L	> 230 g/L
Hematocrit	0.85 × LLN	1.15 × ULN	< 0.24	NA
Red Blood cells	0.85 × LLN	1.15 × ULN	NA	NA
MCV	0.85 × LLN	1.15 × ULN	NA	NA
MCH	0.85 × LLN	1.15 × ULN	NA	NA
MCHC	0.85 × LLN	1.15 × ULN	NA	NA
Platelets	0.85 × LLN	1.15 × ULN	< 100 × 10 ⁹ /L	NA
White Blood cells				
Total	0.85 × LLN	1.15 × ULN	< 1 × 10 ⁹ /L	> 30 × 10 ⁹ /L
Neutrophils	0.85 × LLN	1.15 × ULN	< 0.5 × 10 ⁹ /L	NA
Eosinophils	NA	1.15 × ULN	NA	NA
Basophils	NA	1.15 × ULN	NA	NA
Lymphocytes	0.85 × LLN	1.15 × ULN	NA	NA
Monocytes	NA	1.15 × ULN	NA	NA

Table 3 Expanded normal ranges and notable abnormalities for laboratory parameters

Laboratory Parameter	Expanded Normal Ranges		Notable Abnormalities	
	Lower Limit	Upper Limit	Lower Limit	Upper Limit
BIOCHEMISTRY				
Aspartate aminotransferase	NA	1.15 × ULN	NA	> 3 × ULN
Alanine aminotransferase	NA	1.15 × ULN	NA	> 3 × ULN
Alkaline phosphatase	NA	1.15 × ULN	NA	> 3 × ULN
Gamma-glutamyltranspeptidase	NA	1.15 × ULN	NA	> 3 × ULN
Total bilirubin	NA	1.15 × ULN	NA	> 51.3 µmol/L
Creatine-kinase	NA	1.15 × ULN	NA	> 10 × ULN
Lactate dehydrogenase	NA	1.15 × ULN	NA	> 3 × ULN
Blood urea nitrogen	NA	1.15 × ULN	NA	> 17.9 mmol/L
Creatinine	NA	1.15 × ULN	NA	> 265 µmol/L
Uric acid	NA	1.15 × ULN	NA	> 714 µmol/L
Total cholesterol	NA	1.15 × ULN	NA	NA
Triglycerides	NA	1.15 × ULN	NA	NA
Glucose	0.85 × LLN	1.15 × ULN	< 2.22 mmol/L	> 22.2 mmol/L
Sodium	0.95 × LLN	1.05 × ULN	< 115 mmol/L	> 165 mmol/L
Potassium	0.95 × LLN	1.05 × ULN	< 2.6 mmol/L	> 6.9 mmol/L
Calcium	0.85 × LLN	1.15 × ULN	< 1.25 mmol/L	> 3.25 mmol/L
Chloride	0.95 × LLN	1.05 × ULN	NA	NA
Inorganic phosphorus	0.85 × LLN	1.15 × ULN	NA	NA
Total Protein	0.85 × LLN	1.15 × ULN	< 20 g/L	> 90 g/L
Albumin	0.85 × LLN	1.15 × ULN	NA	NA
URINALYSIS				
pH	0.85 × LLN	1.15 × ULN	NA	> 1.15 × ULN

MCH = mean corpuscular haemoglobin; MCHC = mean corpuscular haemoglobin concentration; MCV = mean corpuscular volume; LLN = lower limit of normal; ULN = upper limit of normal (LLN and ULN values are provided by the laboratory). NA = Not applicable

4.4.1.3 ECG

All ECG data collected will be listed.

Mean absolute values and mean change from baseline for continuous ECG parameters will be summarised by treatment, day (Day 1, 8, and 14) and timepoint within day, 95% CIs for the change from baseline will be provided in addition to the usual descriptive statistics parameters.

Graphical presentation of mean change from baseline (and SE) for ECG parameters by treatment and timepoint will also be provided.

For HR, and QTcF parameters, change from baseline at each timepoint within Day 1, Day 8, and Day 14 will be analysed by means of a mixed model; a random effect model with fixed effects for treatment, sequence, and period. The patient will be fitted as a random effect and the pre-dose value of the parameter obtained at visit 3 will be included as a covariate. Between-groups difference in LSM means will be provided with their 90% CI. A Figure presenting the LSM means and 90% CI across time will be presented as well.

QTcF exceeding ICH boundaries are defined in Table 4. Other ECG values (HR, QRS interval, and PR interval) are defined to be PCS if they meet criterion 1 or criterion 2 displayed in Table 5. Number and percentages of patients with post-baseline QTcF exceeding ICH boundaries and PCS ECG values will be presented for each category, each criterion defined in Table 4 and Table 5.

These numbers and percentages of patients with post-baseline QTcF exceeding ICH boundaries and PCS ECG values will be summarised by treatment overall and by timepoint within each day (Day 1, 8, and 14).

A listing of individual data for all patients with PCS ECG values will be provided, and will include treatment sequence, patient number, and all ECG values (baseline and post-baseline values), clinical relevance of PCS assessed by the PI will also be in the listing.

A listing of all treatment-emergent AEs recorded for patients with PCS ECG values (at baseline or post-baseline) will also be provided.

The number and percentage of patients with post-baseline abnormal ECG findings (Rhythm, Extra Systoles, Conduction, ST-Changes, ST Segment, T Wave Observations, and U Wave Observations) will be summarised by treatment, overall and by timepoint within each day (Day 1, 8, and 14).

Percentages will be based on the number of patients with at least one post-baseline ECG assessment.

A listing of all ECG abnormal findings will be provided.

Table 4 PCS ECG criteria: QTcF exceeding ICH boundaries


Category 1: QTcF value above the following cut-off at any time during treatment
 
Criteria:
 
 >450 (ms) >480 (ms) >500 (ms) 
Category 2: QTcF increase by more than following cut-off at any time during treatment
 
Criteria:
 
 >30 (ms) >60 (ms) >90 (ms) 
Category 3: QTcF value above cut-off and QTcF increase by more than cut-off at any time during treatment
 
Criteria:
 
 Value >450(ms) and Increase >30(ms) Value >500(ms) and Increase >60(ms)
--

Table 5 PCS ECG criteria: Heart Rate and QRS interval

ECG parameter	Category	Criterion 1	Criterion 2
Heart rate	Tachycardia event	≥ 110 bpm and an increase of $\geq 15\%$ over baseline value	≥ 120 bpm if baseline is < 100 bpm
	Bradycardia event	≤ 50 bpm and a decrease of $\geq 15\%$ over baseline value	≤ 40 bpm if baseline is > 40 bpm
QRS interval		≥ 100 msec and an increase of $\geq 25\%$ over baseline value	≥ 150 msec if baseline is < 150 msec
PR interval		≥ 200 msec and an increase of $\geq 25\%$ over baseline value	≥ 250 msec if baseline is < 250 msec

bpm = beats per minute.

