4.1.2 Presentation of results

All analyses will use SAS® version 9.3 or higher. Unless otherwise specified, summary tables will be presented by treatment group, labelled as follows: AZD8871 600 µg, Anoro® Ellipta®, and Placebo.

All data will be presented in listings, sorted by sequence, patient number, and treatment. Continuous variables will be summarised by the number of observations, mean, standard deviation (SD), median, minimum, and maximum. Categorical variables will be summarized by frequency counts and percentages for each category. Unless otherwise stated, percentages will be calculated out of the population total for the corresponding treatment.

The minimum and maximum will be reported to the same number of decimal places as the raw data recorded in the database. The mean, median and standard deviation will be reported to one more decimal place than the raw data recorded in the database. The maximum number of decimal places presented for any statistic shall be four, except for pulmonary function variables, where the maximum shall be three. Decimals to be used for PK analysis is described in section 4.3.

Percentages will be presented to one decimal place.

All confidence intervals (CIs) will be two-sided 95% CIs, unless stated otherwise, and presented to one more decimal place than the raw data recorded in the database. If a model is used to estimate the treatment difference, the corresponding CI according to the model will be presented. Otherwise, the unadjusted CI will be used. Nominal p-values may also be presented. Care should be taken when interpreting CIs and p-values since no correction for

multiple testing is done for the endpoints. The presentation of p-values- will be to four decimal places unless a p-value is less than 0.0001, in which case “<0.0001” will be displayed.

A month and a year are operationally defined to be 30.4 and 365.25 days respectively.

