4.4.1.4 Vital signs

All vital sign data collected will be listed.

Mean absolute values and mean change from baseline for BP will be summarised by treatment, and time point; graphical presentation of mean change from baseline and SE will be provided also.

High and low PCS vital signs values will be identified. Vital sign values will be PCS if they meet both the PCS criteria for the observed value and the PCS criteria for the change from baseline value for criterion 1, or if they meet the PCS criteria for the observed value for criterion 2; the 2 criteria should not be combined. The criteria for PCS vital signs values are displayed in Table 6.

Table 6 PCS vital sign criteria

		Criterion 1		Criterion 2
Vital sign		Observed value	Change from baseline	Observed value
Systolic BP (mmHg)	High	≥ 180	Increase of ≥ 20	≥ 200 , if baseline < 160
	Low	≤ 90	Decrease of ≥ 20	≤ 75 , if baseline > 75
Diastolic BP (mmHg)	High	≥ 105	Increase of ≥ 15	≥ 115 , if baseline < 115
	Low	≤ 50	Decrease of ≥ 15	≤ 40 , if baseline > 40

BP = Blood pressure.

The number and percentage of patients with post-baseline PCS vital sign values will be summarised for each criteria by treatment, day and timepoint within day. Percentages will be based on the number of patients with baseline vital sign values and at least one post-baseline vital sign assessment.

A listing of individual data for all patients with PCS vital sign values will be provided, and will include treatment sequence, patient number, and all vital sign values (baseline and post-baseline values).

A listing of all treatment-emergent AEs recorded for patients with PCS vital sign values (at baseline or post-baseline) will also be provided.

CCI

[REDACTED]

[REDACTED]

CCI

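### Time-point percentages for abnormal ECG, blood pressure and laboratory values are divided by groups that include patients not measured at that time point, and blood pressure has no any-time row

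*SAP*

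**What the plan says.** **ECG (SAP 4.4.1.3).** Counts and percentages of patients with QTcF above the ICH boundaries and with potentially clinically significant (PCS) ECG values "will be summarised by treatment overall and by timepoint within each day (Day 1, 8, and 14". Abnormal ECG findings are tabulated on the same grid. One denominator sentence follows the abnormal-findings paragraph: "Percentages will be based on the number of patients with at least one post-baseline ECG assessment". It does not say whether it also governs the QTcF and PCS tables.

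**Blood pressure (SAP 4.4.1.4).** PCS values "will be summarised for each criteria by treatment, day and timepoint within day". No row for any time on treatment is planned. The denominator is again an any-time one, here with a baseline requirement: "Percentages will be based on the number of patients with baseline vital sign values and at least one post-baseline vital sign assessment".

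**Laboratory and i-STAT (SAP 4.4.1.2).** "Shift from baseline tables will be presented by treatment overall and by timepoint", with low, within and high categories relative to the expanded normal range. No denominator is given, so the rule in SAP 4.1.2 applies: "Unless otherwise stated, percentages will be calculated out of the population total for the corresponding treatment".

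**Who is in the population and who is measured.** One dose of a treatment puts a patient in the safety set for that treatment (SAP 2.1.2). A patient who stops treatment is excused the remaining planned visits, apart from a Follow-up Visit 42 to 49 days after the last dose (Protocol 7.1.3). Missing safety data are in general not imputed (Protocol 9.4).

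**The concern.** A percentage for one time point should be read against the patients measured then. Under these rules, a patient with a Day 1 post-dose reading who then stops remains in the Day 8 and Day 14 denominators for that treatment but can no longer enter the numerator. Late percentages are therefore too low, and lower for a treatment that loses more patients during dosing.

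The variables concerned are not neutral. Findings in systolic pressure, potassium, heart rate and QTcF are themselves withdrawal criteria (Protocol 7.1), and cardiac effects and hypokalaemia are named potential risks (Protocol 2.3). Stopping may therefore be related to what is being tabulated.

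A smaller mismatch is that the ECG denominator lacks the baseline requirement that the blood pressure section has, although Table 4 categories 2 and 3 and every Table 5 criterion need a baseline. Little should turn on this, because a pre-dose ECG is scheduled on Day 1 of every period (Protocol Table 1, footnote h).

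**Working it through.** **Step 1. Rule against row.**

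| Table | Rows planned | Denominator under the SAP | Fits time-point rows? |
|---|---|---|---|
| Abnormal ECG findings | overall and by time point | any post-baseline ECG | no |
| QTcF and PCS ECG | overall and by time point | the same or, if that sentence covers only abnormal findings, treatment population total | no |
| PCS blood pressure | by day and time point only | baseline plus any post-baseline reading | no |
| Laboratory, i-STAT | overall and by time point | treatment population total (default) | no |

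Either reading of the ECG sentence gives dilution. The default gives at least as much, because it also keeps dosed patients who have no post-baseline ECG.

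**Step 2. Inputs.** The plan gives no figure for these tables. Its dropout figure reproduces: 54 / (1 − 0.25) = 72 randomised, so 18 losses (Protocol 9.2). The earlier three-way crossover in COPD lost 42 − 31 = 11 of 42, or 26% (Protocol 2.3). The split of losses between dosing and wash-out is not given, so it is varied below.

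**Step 3. Formula.** Displayed % = % among patients measured × (number measured at the time point / denominator).

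Assume equal retention in each period: 0.75^(1/3) = 0.9086. Starters by period are then 72, 65.4 and 59.4, a total of 196.8 and an average of 65.6 per treatment. Losses total 18, so 18 / 196.8 = 0.0914. Let s be the share of losses that fall inside dosing, after a first post-baseline reading and before the Day 14 reading. Then measured / denominator = 1 − 0.0914 × s.

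**Step 4. A value of s proportional to time.** Dosing is 3 × 14 = 42 days and the two wash-outs are 84 to 98 days. This gives s = 42/126 = 33% down to 42/140 = 30%.

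**Step 5. Results for a 10% rate among patients measured at Day 14.**

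| Share of losses within dosing | Measured / denominator | Displayed |
|---|---|---|
| 0% | 1.000 | 10.0% |
| 25% | 0.977 | 9.8% |
| 30–33% (proportional to time) | 0.973–0.970 | 9.7% |
| 50% | 0.954 | 9.5% |
| 100% | 0.909 | 9.1% |

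Whole numbers agree for the last row: 6 losses per period give (66 + 60 + 54) / (72 + 66 + 60) = 180/198 = 0.909.

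**Step 6. Unbalanced losses.** If all 72 start a treatment and L stop during it, 10% displays as 10 × (72 − L)/72. That is 9.2% for L = 6, 8.3% for L = 12 and 7.5% for L = 18. The last figure puts every planned loss in the trial on one treatment.

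**Step 7. Laboratory categories.** A patient without a sample is in none of low, within or high. The three percentages therefore sum to the ratio in Step 5: about 97% if losses are proportional to time, and 91% if all fall within dosing. Safety laboratory tests have one scheduled on-treatment post-baseline sample per period, 24 hours after the Day 14 dose. i-STAT has several time points on Days 1 and 14 (Protocol Table 1, footnotes j and k).

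**The case against.** The strongest reply is that nothing is hidden. Counts accompany percentages, and continuous summaries by time point give the number of observations (SAP 4.1.2). The heart rate and QTcF mixed models do not use these denominators. Patients with PCS ECG or blood pressure values are listed individually with their adverse events. Treatment-emergent events leading to discontinuation are tabulated (SAP 4.4.1.1). The study is exploratory and no decision rule uses these percentages. All of this stands, and it keeps the stakes low. It does not make the written denominators right for the rows they serve. To say that a programmer would use the number measured anyway is to say that the SAP would not be followed.

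Two stronger readings are tempting, and the documents support neither.

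- *Patients who stop early are counted as normal, or as showing no shift.* A reader might infer this from the denominators. No section assigns a missing value to a category. The laboratory categories are explicit, and an unmeasured patient falls in none of them. The effect is dilution, not misclassification.
- *Dividing by patients measured would expose a treatment that causes stops.* It would not, because it removes stoppers from numerator and denominator alike. As an assumed illustration, take 72 treated patients, of whom 8 stop on Day 1 for QTcF and 3 others are flagged at Day 14. The Day 14 row is 3/72 = 4.2% under the SAP and 3/64 = 4.7% when corrected. The any-time row is 11/72 = 15.3%, and only that row shows the 8. The SAP already plans overall rows for ECG and laboratory data. Blood pressure is the gap.

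**Conclusion.** The concern holds as a matter of denominators. Time-point percentages for ECG, blood pressure, laboratory and i-STAT abnormalities are to be divided by groups that include patients not measured at that time point, so Day 8 and Day 14 figures are diluted. The effect is confined to the treatment being taken when the patient stopped, because the safety set leaves out treatments never started.

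The size is modest. A 10% rate shows as about 9.7% at Day 14 if the planned 25% dropout is even across periods and proportional to time, and as 9.1% if every loss falls within dosing. The 7.5% figure is an extreme, not an expectation. All of these rest on an assumed timing of dropout that the documents do not give.

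The more useful omission is the any-time blood pressure row, since any-time rows are where early abnormalities that lead to stopping appear. The SAP should be corrected before the tables are programmed. The primary analysis is unaffected.

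**What to change.** In SAP 4.4.1.2, 4.4.1.3 and 4.4.1.4:

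- **Time-point rows:** divide by patients in that treatment period with a value at that time point, and with a baseline where the criterion needs one. Print that n in the row.
- **Overall rows:** divide by patients with at least one post-baseline value in that treatment period, and with a baseline where needed.
- **PCS vital signs:** add an any-time row for each criterion by treatment.
- **Scope:** state that the ECG rule covers the QTcF, PCS and abnormal-findings tables, and that all of these rules override the SAP 4.1.2 default.

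The cost is SAP wording and table-shell edits, with no new data. Denominators will vary from row to row, and some percentages will be slightly less favourable.
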